### 6.2 OUTCOME MEASURES

*Primary efficacy endpoint:* major adverse cardiac event (MACE), defined as any of the following: cardiovascular death, myocardial infarction, emergency revascularisation, hospitalisation for unstable angina.

*Primary safety endpoint:* the above MACE endpoint plus complications from cardiac diagnosis or treatment including major bleeding requiring transfusions or hospitalizations, vascular intervention subsequent to cardiac interventions stroke and all-cause death.

*Secondary endpoints:* death, cardiovascular death, procedure-related death, myocardial infarction, emergency revascularisation, stroke, hospitalisation with unstable angina, hospitalisation with heart failure, hospitalisation with arrhythmia, major bleeding, health-related quality of life (QoL), time off list (including number of temporary suspension and duration of each suspension), cost-effectiveness, incidence of permanent removal from list for cardiac causes; incidence of transplantation and cancellation of transplant due to CAD.

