**Table 2: Outcome definitions**

Outcome	Definition (31-32)
Cardiovascular death	Cardiovascular death is defined as any death with a cardiovascular cause and includes those deaths after a cardiovascular procedure (eg, percutaneous coronary intervention), cardiac arrest, myocardial infarction, pulmonary embolus, stroke, and haemorrhage or deaths due to an unknown cause. Non cardiovascular death is defined as any death owing to a clearly documented non cardiovascular cause (eg, trauma, infection, malignancy).
Myocardial infarction	Myocardial Infarction (MI) is defined as the presence of any 1 of the

[figure not shown]
	
following 3 criteria:
 
 
1. A typical rise of troponin or a typical fall of an elevated troponin detected at its peak post-surgery in a patient without a documented alternative explanation for an elevated troponin (e.g. pulmonary embolus) OR a rapid rise and fall of CK-MB. This criterion also requires that 1 of the following must also exist:           
 
a. Ischemic signs or symptoms (i.e., chest, arm, neck, or jaw discomfort; shortness of breath, pulmonary edema)
 
b. Development of pathologic Q waves present in any two contiguous leads that are <math>\geq</math> 30 milliseconds
 
c. ECG changes indicative of ischemia (i.e. ST segment elevation [<math>\geq</math> 2mm in leads V1, V2, or V3 OR <math>\geq</math> 1mm in other leads], ST segment depression [<math>\geq</math> 1mm], or symmetric inversion of T waves <math>\geq</math> 1mm) in at least two contiguous leads
 
d. Coronary artery intervention (i.e., PCI or CABG surgery)
 
e. New or presumed new cardiac wall motion abnormality on echocardiography or new or presumed new fixed defect on radionuclide imaging
 
 
 
2. Pathological findings of an acute or healing myocardial infarction
 
3. Development of new pathological Q waves on an ECG if troponin levels were not obtained or were obtained at times that could have missed the clinical event
 

Emergency revascularisation	Emergency revascularisation within 1 month of presentation of new or progressive symptoms of coronary artery disease

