## 7.2 STUDY TYPE & DESIGN & SCHEDULE

This trial is a pragmatic multi-centre, randomized, parallel group definitive trial incorporating an economic evaluation and involving sites in Canada, Australia and New Zealand. Asymptomatic waitlisted patients will be randomised to no screening versus routine screening for CAD (i.e. Exercise Stress test, Myocardial Perfusion Scintigraphy or Dobutamine Stress Echo) as per the current standard of care at each centre.

**Intervention:** Patients randomized to no screening will **not** undergo regular non-invasive testing for CAD while on the wait list.

**Control:** Patients randomized to routine screening will undergo non-invasive testing for CAD every year or second yearly as determined by local centre practice.

**All:** Patients in either group who develop symptoms of angina or an angina equivalent at any stage will be investigated according to the local standard of care, which may include the use of non-invasive or invasive cardiac testing.

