#### 7.4 STANDARD CARE AND ADDITIONAL TO STANDARD CARE PROCEDURES

**Management of patients who develop clinical symptoms of CAD:** Any patient, regardless of randomised trial allocation, developing clinical symptoms of CAD (e.g. angina, congestive heart failure, or new arrhythmias) will be evaluated according to the standard of care in individual transplant centres *and may include the use of non-invasive cardiac stress testing.* Management of symptomatic CAD including revascularization will be according to the standard of care at the local transplant centre.

Other than the use of cardiac screening tests, patient management will be as per the usual standard of care in participating transplant centres. In both study groups, the frequency and content of clinical re-evaluations will be according to the existing practice of the transplant centres participating in the study. Such evaluations may include cardiology consultations. Clinical evaluations by the transplant centre during wait-listing will be recorded in both groups. Interventions to prevent cardiovascular disease events may be used. Study personnel will document all surgical and medical interventions for CAD. The use of cardio-protective medications (aspirin, beta-blockers, medications that block activation of the renin angiotensin system, lipid lowering agents) will be documented every six months in all trial participants. However, the use of lipid lowering agents, aspirin, and beta-blockers remain controversial due to the lack of definitive evidence regarding efficacy in ESKD patient, and their use is likely to vary between centres and between physicians at the same centre.(9, 34) Similarly behavioural therapies such as participation in weight loss, smoking cessation or healthy heart programs may be used. Medical and behavioural treatments will not be specified in the trial but will be documented by study personnel.

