## **11. DATA SECURITY & HANDLING**

### **11.1 DETAILS OF WHERE RECORDS WILL BE KEPT & HOW LONG WILL THEY BE STORED**

Data will be captured using REDCap and stored on servers at the Sydney Local Heath District (SLHD) Royal Prince Alfred data centre. Participating sites will enter data into electronic case report forms (eCRF) via a secure web-based data capture software tool. REDCap allows data to be inputted at multiple sites with web authentication, data logging and Secure Sockets Layer encryption. Records will be kept for a minimum of 15 years.

The coordinating site will generate periodic data audit for quality and accuracy and provide data reports required for progress reports, data safety monitoring board meetings and event adjudication committee meetings.

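### MI criterion 3 counts new Q waves without symptoms as a primary event, and only the control arm has planned stress tests, so an excess of detected silent MIs there would favour non-inferiority

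*Protocol*

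**What the plan says.** Protocol section 6.2 defines the primary efficacy endpoint, MACE, as any of "cardiovascular death, myocardial infarction, emergency revascularisation, hospitalisation for unstable angina". Table 2 in the same section says that meeting one of three criteria is enough for an MI. The third is "Development of new pathological Q waves on an ECG if troponin levels were not obtained". A second limb of that criterion covers troponins taken too early or too late to catch the event.

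Section 7.2 fixes the difference between the arms. In the control arm, "Patients randomized to routine screening will undergo non-invasive testing for CAD every year or second yearly as determined by local centre practice"; the tests named are "Exercise Stress test, Myocardial Perfusion Scintigraphy or Dobutamine Stress Echo". Patients in the no-screening arm do not "undergo regular non-invasive testing for CAD while on the wait list". Other contacts are common to the arms: "In both study groups, the frequency and content of clinical re-evaluations will be according to the existing practice" of each centre (section 7.4). The study schedule (Table 4) lists no ECG in either arm.

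Section 10.3 takes the screening arm as the referent and claims non-inferiority if the whole 95% CI for the HR lies below 1.25. Section 11.1 mentions "event adjudication committee meetings" but gives no rule for infarcts seen only on an ECG.

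**The concern.** An asymptomatic outpatient will usually have had no troponin measured, so the condition in criterion 3 is normally met by default. New Q waves on an ECG recorded at a planned stress test then make a dated primary event. The procedure being randomised thus also helps to detect the endpoint, and it is scheduled in one arm only.

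Silent infarcts are plausible here. Section 5.2 says that people with ESKD may lack classic symptoms, and it reports chest pain at presentation in 44% of dialysis patients hospitalised with MI against 68% of non-dialysis patients.

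Extra events in the referent arm push the HR down. In a non-inferiority trial that is the anti-conservative direction. Intention-to-treat analysis does not correct it, because the difference follows the randomised arm. Adjudication does not either, because such a case meets the definition as written.

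**Working it through.** **1. Is criterion 3 the only way in?** From Table 2:
- Emergency revascularisation requires new or worsening symptoms.
- Unstable angina requires an unscheduled hospital stay.
- MI criterion 1 requires a biomarker change, so a new fixed defect or wall motion abnormality at a screening test does not count alone.
- MI criterion 2 requires pathological findings.
- MI criterion 3, no-troponin limb, requires only new Q waves.

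So, of the non-fatal components, only criterion 3 lets a finding at a planned outpatient test become MACE with no biomarker change and no presentation.

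**2. The plan's own power figure.** Inputs from section 10.2: margin 1.25, two-sided 5%, 80% power, MACE 6% per year, N = 3306, follow-up of 4 years (Australasia, 1100 patients) and 5 years (Canada, 2206), 10% drop-out. Allocation of 1:1 is assumed.

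Events needed (Schoenfeld): D = 4(1.96 + 0.8416)² / (ln 1.25)² = 630.5, about 631.

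Events expected with hazard 0.06, full follow-up and 10% loss per year (loss hazard 0.105): 1100 × 0.1756 + 2206 × 0.2041 ≈ 643, giving 80.8% power. One-year accrual with a one-off 10% loss gives 657 events and 81.6%; two-year accrual gives 585 and 77.0%. The accrual length is not stated. The stated 80% is reproduced under reasonable assumptions, so 631 is a fair working number.

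**3. Decision threshold.** SE(ln HR) = 2/√630.5 = 0.0797. Non-inferiority is claimed if the estimated HR is below exp(0.2231 − 1.96 × 0.0797) = 1.069.

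**4. Effect of a net control-arm excess.** Let s be the net proportional addition to control MACE. It is an assumption, since the documents give no rate.

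Observed HR = 1.25/(1 + s)

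P(claim) = Φ((ln 1.069 − ln observed HR)/0.0797) = Φ(−1.96 + ln(1 + s)/0.0797)

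Extra patients are s × 315 (half of 631), out of 3306/2 = 1653 per arm.

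| s | Extra control patients | Share of 1653 | Observed HR | False non-inferiority |
|---|---|---|---|---|
| 0 | 0 | 0 | 1.25 | 2.5% |
| 3% | about 9 | 0.6% | 1.21 | 5.6% |
| 5% | about 16 | 1.0% | 1.19 | 8.9% |
| 10% | about 32 | 1.9% | 1.14 | 22.3% |

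**5. Check on the approximation.** At a true HR of 1.25 the events split unequally: 631/2.25 ≈ 280 in the control arm. Using that split and adding the extra events to the control count gives 9.0% at s = 5% (14 extra patients) and 23.0% at s = 10% (28 extra). The result does not depend on the simplification.

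**The case against.** The strongest reply is that no-screening patients also have ECGs. Local re-evaluations may include cardiology consultations (section 7.4), symptoms are worked up in both arms, hospital and transplant admissions are recorded, and about half the participants are expected to be transplanted (section 10.2). Q waves often persist, so an infarct missed early may be found later. This stands. A reader might infer that such MIs occur in the control arm alone and stay unseen in the other; the documents do not support that. They support an excess and earlier dating.

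The ECG at each test is inferred from the nature of the tests and is not written in the protocol. Nor is it stated that the tracing would be compared with an older one and reported as an MI. This limits certainty about the size of the effect but not about its direction.

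The size is hypothetical, and s is a net figure. If about half of these infarcts were eventually recorded in the no-screening arm, a 5% net excess would need roughly 10% detected in the control arm. Some patients would have had a later MACE anyway. Tests are one to two years apart, can be missed (CRF9), and adherence in the first phase was hypothesised at 90% (section 5.2). All of this dilutes the effect.

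The mistimed-troponin limb of criterion 3 refers to a clinical event, which might suggest that a presentation is intended throughout. That wording belongs to the second limb; the no-troponin limb carries no such condition. If one was meant, Table 2 should say so.

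Finally, keeping silent infarcts in the endpoint is defensible on clinical grounds, but it needs similar ascertainment in both arms. Adjudication guidance and sensitivity analyses may sit in documents not shown, so their absence is not held against the plan. The endpoint definition, however, is fixed in Table 2.

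**Conclusion.** The point holds as a matter of differential ascertainment. Criterion 3 admits symptomless Q-wave MIs to the primary endpoint, and the planned tests give the control arm more scheduled opportunities to find them. The likely bias is towards non-inferiority.

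Its size cannot be set from the documents. The false-claim rates of about 6%, 9% and 22% are illustrations at assumed net excesses of 3%, 5% and 10%, with about 631 events, 1:1 allocation and a true HR at the margin. A reader might take them as an estimate of the trial's actual error rate; without a silent-MI rate they are not. They do show that about 16 extra control patients, 1% of the arm, would be enough to matter against this margin. The direction is clear, the size is uncertain and the remedy is cheap, so the change should be made.

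**What to change.** In Table 2, count criterion 3 in primary MACE only when the ECG was recorded for a clinical presentation, with the same rule in both arms. Report Q-wave-only MIs without a presentation as a separate silent-MI outcome, by arm.

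If the definition is kept, pre-specify a sensitivity analysis of the primary HR that excludes all criterion-3-only MIs without a clinical presentation, in both arms. It should not exclude only those first seen at a planned screening test (CRF7). That would remove essentially control events alone, while the same infarct in a no-screening patient, first seen at a transplant admission, would still count. The HR would then be pushed upwards.

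The cost is one sentence in Table 2 and a matching line in the adjudication guidance. The forms for planned tests (CRF7) and non-fatal MI (CRF13) already exist, and section 11.3 provides for uploading test reports. Patient care does not change. The downside is that a few true silent infarcts leave the primary endpoint, so the event count, and with it the power, falls slightly.

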Hospitalisation with unstable angina	Pain or equivalent with the presence of dynamic ECG changes, that requires hospitalisation. This classification require that 4 separate criteria be met: a) Worsening ischaemic discomfort b) Unscheduled hospitalization c) Objective evidence of myocardial ischaemia and d) Negative cardiac biomarkers
Hospitalization	Hospitalisation is defined as an admission to an inpatient unit or a visit to an emergency department that results in at least a 24-hr stay.
Stroke	A new focal neurologic deficit thought to be vascular in origin with signs and symptoms lasting $>24$ hours or leading to death
Procedure Related Death	Death caused by the immediate complication(s) of a Cardiovascular procedure
Major bleeding	
Bleeding Academic Research Consortium (BARC) type 3 and 5.
 
Type 3a: Overt bleeding plus hemoglobin drop of 3 to <math><5</math> g/dL* (provided hemoglobin drop is related to bleed). Any transfusion with overt bleeding
 
Type 3b: Overt bleeding plus hemoglobin drop <math><5</math> g/dL* (provided hemoglobin drop is related to bleed). Cardiac tamponade. Bleeding requiring surgical intervention for control (excluding dental/nasal/skin/hemorrhoid). Bleeding requiring intravenous vasoactive agents.
 
Type 3c: Intracranial hemorrhage (does not include microbleeds or hemorrhagic transformation, does include intraspinal) Subcategories confirmed by autopsy or imaging or lumbar puncture. Intraocular bleed compromising vision
 
Type 5: fatal bleeding

	Type 5a: Probable fatal bleeding; no autopsy or imaging confirmation but clinically suspicious
	Type 5b: Definite fatal bleeding; overt bleeding or autopsy or imaging confirmation

Definitions adapted from: 2014 ACC/AHA Key data elements and definitions for cardiovascular endpoint events in clinical trials,(30) Rational, design and organization of Perioperative Ischaemic Evaluation (POISE) trial: A randomized controlled trial of metoprolol versus placebo in patients undergoing noncardiac surgery,(31) and Standardised Bleeding Definitions for Cardiovascular Clinical Trials.(32)

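### Table 2 reads type 3b major bleeding as a haemoglobin fall below 5 g/dL, which swallows type 3a and leaves falls of 5 g/dL or more in neither band

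*Protocol*

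**What the plan says.** The Major bleeding row of Table 2 (Protocol, section 6.2) adopts "Bleeding Academic Research Consortium (BARC) type 3 and 5" and then writes the subtypes out.

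- **Type 3a:** "Type 3a: Overt bleeding plus hemoglobin drop of 3 to" below 5 g/dL, where the fall is related to the bleed. A second route is "Any transfusion with overt bleeding".
- **Type 3b:** "Type 3b: Overt bleeding plus hemoglobin drop", followed by below 5 g/dL with the same relatedness condition. Other routes are cardiac tamponade, surgical control (with some sites excluded) and "Bleeding requiring intravenous vasoactive agents".
- **Type 3c and type 5:** intracranial or sight-threatening bleeding, and fatal bleeding.

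The term is used in two endpoints. Section 6.2, and the synopsis in section 4.6, put into the primary safety endpoint "complications from cardiac diagnosis or treatment including major bleeding requiring transfusions or hospitalizations". The secondary endpoint list names the outcome without any qualifier: "hospitalisation with arrhythmia, major bleeding, health-related quality of life (QoL").

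**The concern.** Types 3a and 3b are presented as successive grades, so their haemoglobin bands should adjoin. With the sign as it reads, the higher grade has no lower limit and stops where it should start. Because any type 3 event is a major bleed, this changes who has the outcome and not just which subtype label is recorded.

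Bleeding also bears on the trial's rationale. Table 1 lists added bleeding risk after revascularisation among the harms of screening. An outcome definition that admits negligible falls and omits some of the largest measures that harm poorly. If the extra small bleeds are unrelated to allocation, they would tend to make the arms look alike.

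The definition is fixed in the protocol itself, so it is not a detail left to a statistical analysis plan.

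**Working it through.** No sample size, power or alpha depends on this point, and the plan states no figure to reproduce. The check is a classification of cases under the written rule and under a 3b band that begins at 5 g/dL.

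**Step 1: haemoglobin bands alone** (overt bleeding, fall related to the bleed, no other criterion).

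| Fall (g/dL) | 3a: 3 to <5 | 3b as it reads: <5 | Major as it reads | Major if 3b is ≥5 |
|---|---|---|---|---|
| 0.5, 1, 2, 2.9 | no | yes | yes | no |
| 3, 4, 4.9 | yes | yes | yes | yes |
| 5, 6, 8 | no | no | no | yes |

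As it reads, the combined band is every fall below 5 g/dL. The lower limit of 3 in type 3a then does no work. With 3b starting at 5, the combined band is every fall of 3 g/dL or more, without overlap or gap.

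**Step 2: add the other routes.** Cross falls of 1, 4 and 6 g/dL with transfusion (yes/no), hospitalisation (yes/no) and any other type 3b or 3c criterion (yes/no): 3 × 2 × 2 × 2 = 24 patterns. Transfusion or another criterion makes the event major whatever the fall, so the sign matters only when both are absent.

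- Fall of 1, no transfusion, no other criterion: major as it reads, not major with 3b at ≥5. This covers 2 patterns (with and without hospitalisation).
- Fall of 6, no transfusion, no other criterion: not major as it reads, major with 3b at ≥5. This also covers 2 patterns.
- Fall of 4: no pattern changes.

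So 4 of the 24 patterns change status for Table 2 major bleeding, and hence for the secondary endpoint. These are logical patterns, not patients, and 4/24 is not a frequency.

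**Step 3: the primary safety composite.** Take its bleeding component as Table 2 major bleeding that also needed transfusion or hospitalisation. Of the 4 patterns, the 2 without hospitalisation are outside the composite under either sign. The 2 with hospitalisation still change: a fall of 1 with hospitalisation only is wrongly in, and a fall of 6 with hospitalisation only is wrongly out. Both would also have to be complications of cardiac diagnosis or treatment. If the composite phrase were instead a free-standing rule (transfusion or hospitalisation, whatever Table 2 says), the 3b sign would not matter to the composite at all.

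**Step 4: what does not use the definition.** The MACE components in section 6.2 do not include bleeding. The 1.25 margin and N = 3306 in section 10.2 rest on MACE alone.

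**The case against.** **The sign may be a reading fault.** The text was extracted from a PDF, the table is broken, and the wording after the sign is identical for 3a and 3b, so a program could have repeated it. This cannot be excluded, and the source PDF settles it. Against it, comparison signs elsewhere in Table 2 read correctly: greater-or-equal in the myocardial infarction criteria and greater-than in the stroke row. Those are other cells, so this is supporting evidence and not proof.

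**If printed, it is an obvious slip.** The row names an external standard, and section 11.1 refers to event adjudication committee meetings, so members might apply the intended grade. That lowers the likely harm. It does not correct the written rule.

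**Large falls have other ways in.** True: many such bleeds would be transfused, operated on or otherwise captured. The loss is confined to large falls with none of these features.

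Two stronger readings might be inferred, and the protocol supports neither.

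- *The primary safety endpoint is flooded with trivial bleeds and its hazard ratio measurably diluted.* The composite wording, "major bleeding requiring transfusions or hospitalizations", filters out most of them, as step 3 shows. The protocol gives neither a bleeding rate nor an expected safety hazard ratio from which a dilution could be computed.
- *The protocol holds two contradictory bleeding definitions.* The composite wording reads naturally as a restricted subset of the Table 2 term, which is ordinary drafting. The protocol does not say so, which justifies a clarification. Replacing the phrase by full Table 2 bleeding would be a preference, and it would remove the filter.

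**Conclusion.** The type 3b haemoglobin threshold is wrong on the table's own terms as the text reads. It overlaps all of 3a, has no lower limit and leaves falls of 5 g/dL or more in neither band. The main consequence is misclassification of the secondary endpoint of major bleeding. On haemoglobin alone, falls below 3 g/dL are counted and falls of 5 g/dL or more are not. The consequence for the primary safety endpoint is smaller: it is limited to hospitalised, untransfused bleeds with no other qualifying criterion, arising from cardiac diagnosis or treatment.

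This rests on two assumptions: that the sign is printed as it reads here, and that sites or adjudicators apply it literally. The numerical effect on any estimate cannot be derived from the protocol. The primary efficacy analysis and its sample size are unaffected. It should be corrected because it sits in an operative outcome definition and the correction is cheap.

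**What to change.** 1. Check the type 3b sign against the source PDF. If the PDF shows a greater-or-equal sign, nothing further is needed on the threshold.
2. If it is printed as it reads, change 3b to a fall of 5 g/dL or more, so that it begins where 3a ends.
3. See whether the bleeding form (CRF16 in Table 4) and the adjudication instructions repeat the error, and correct them if so. Neither is shown in the protocol, so this is conditional.
4. As a minor clarification in sections 4.6 and 6.2, state that the bleeding component of the primary safety endpoint is the subset of Table 2 major bleeding that required transfusion or hospitalisation.

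The cost is one symbol and one sentence, the sentence being entered in both sections. If the form or instructions carried the wrong threshold, bleeds already classified under it would need to be looked at again.
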